1. BACKGROUND

CB-03-01 (cortexolone 17 α -propionate) is a steroidal antiandrogen that is being developed as a 1% cream for the topical treatment of acne vulgaris, an androgen-dependent skin disorder. CB-03-01 binds to the human androgen receptor displacing the androgenic hormones and acts as an androgen antagonist. In human plasma, CB-03-01 is rapidly metabolized to parent cortexolone so that its systemic bioavailability after topical application is anticipated to be low. Cortexolone, the main by-product, is a physiological component of the pool of endogenous corticosteroids, and is an intermediate in the synthesis of glucocorticoids, but it only exhibits weak glucocorticoid properties [1].

In single-dose studies in mouse and in rat, and following repeated subcutaneous administration in rats, and dermal administration in rabbits and minipigs, the drug was well tolerated with no significant local or unexpected systemic effects. CB-03-01 is not mutagenic in the Ames test or in the human chromosome aberration test, and it is not a skin sensitizer.

To date, four Phase 1 and three Phase 2 clinical studies have been completed with CB-03-01 cream in Europe and the United States, with over 500 subjects exposed to CB-03-01 creams. All studies were conducted using CB-03-01 cream, 1%; additional concentrations of CB-03-01 cream (0.1% and 0.5%) were also used in the most-recent Phase 2 Dose-Escalating study. The studies included:

1. A Phase 1 Single Dose Pharmacokinetics (PK) Study in 24 healthy volunteers [randomized, double-blind, vehicle-controlled, single-ascending dose],
2. A Phase 1 Repeat Dose PK Study in 24 healthy volunteers [randomized, vehicle-controlled, 14-day repeat-dose],
3. A Phase 1 Steady State PK Study in 8 subjects with acne vulgaris [single center, open-label, pilot, 6-week repeat-dose]
4. A Phase 1 Three-week Cumulative Skin Irritation Study in 36 healthy volunteers,
5. A Phase 2 Hypothalamic-Pituitary-Adrenal axis (HPA)/PK study in 42 subjects with acne vulgaris [open-label, 14-day repeat-dose]
6. A Phase 2 Comparator Proof of Concept Study in 72 adult subjects with facial acne vulgaris [randomized, double-blind, vehicle-controlled, active-comparator (Retin-A[®] [tretinoin] 0.05% cream), 8-week repeat-dose], and
7. A Phase 2 Dose-Escalating Study in 363 subjects with facial acne vulgaris [multi-center, randomized, double-blind, vehicle controlled, 12-week repeat-dose]

Overall, the data that resulted from the completion of the aforementioned studies has demonstrated that CB-03-01 creams selected for clinical development (a) are well tolerated locally, (b) result in minimal systemic exposure when applied topically, (c) have a clinical safety profile without any concern and similar to the placebo, and (d) at 1%

concentration applied BID are significantly more effective than its vehicle at reducing inflammatory and non-inflammatory lesions counts in adolescent and adult subjects.

CB-03-01 could offer advantages over existing products for acne vulgaris due to its potential efficacy and lack of systemic antiandrogen activity. Because its pharmacological action appears to be limited to the local site of application, use of CB-03-01 may be able to mitigate the side effects related to systemic exposure to hormonal agents currently used in the treatment of acne.

2. RATIONALE

The concentration of CB-03-01 selected for the initial clinical studies (1%) was based on antiandrogenic activity in the hamster flank organ test in which the best effective concentration was 0.8% [1]. The results of the Phase 2 Dose Escalation Study demonstrated that CB-03-01 cream, 1% applied BID had more favorable results than other treatments (0.1% BID, 0.5% BID, and 1% QD) and no material safety issues were noted with any of the concentrations of CB-03-01 cream [2]. Based on the collective findings of the previous Phase 1 and Phase 2 studies, CB-03-01 cream, 1% BID appears to be the best treatment candidate to advance for further clinical study and development as a topical treatment for acne vulgaris. Thus, the present Phase 3 study has been designed to determine and compare the efficacy of treatment with CB-03-01 cream, 1% and the vehicle cream applied twice daily for 12 weeks in subjects with moderate to severe facial acne vulgaris.

3. OBJECTIVE

The primary objective of this study is to determine the safety and efficacy of CB-03-01 cream, 1% versus the vehicle cream applied twice daily for 12 weeks in subjects with facial acne vulgaris.

4. STUDY DESIGN

This is a multicenter, randomized, double-blind, vehicle-controlled, parallel-group comparison study of safety and efficacy for CB-03-01 cream, 1% in male and female subjects, 9 years or older with moderate to severe acne vulgaris on the face. Eligible subjects must have acne vulgaris of the face (which can include the nose) with an Investigator's Global Assessment (IGA) score of 3 or 4, at least 30 to a maximum of 75 inflammatory lesions (papules, pustules, and nodules), and at least 30 to a maximum of 100 non-inflammatory lesions (open and closed comedones). At least 700 subjects will be enrolled at approximately 40 sites. Subjects will be randomized in a 1:1 ratio to one of two treatment groups:

1. CB-03-01 (cortexolone 17 α -propionate) cream, 1%
2. Vehicle cream

All subjects will apply the assigned test article to the face twice daily for 12 weeks (see Section 6).

In addition, a separate open-label long-term extension study is planned. Subjects completing the treatment-phase of this trial will be offered the opportunity to participate in this follow-on study (CB-03-01/27: An Open-Label, Long-Term Extension Study to Evaluate the Safety of Cortexolone 17 α -Propionate (CB-03-01) Cream, 1% Applied Twice Daily for up to 12 Months in Subjects with Facial Acne Vulgaris). In this open label study, all subjects will apply the active medication (cortexolone 17 α -propionate cream, 1%) twice daily for up to 9 additional months of treatment (for a total of up to 12 months; 0 or 3 months in the pivotal Phase 3 trial and an additional 9 months in the open-label long-term extension study).

5. STUDY POPULATION

5.1 Subject Eligibility

To be included in the study, subjects must meet the following inclusion criteria and none of the exclusion criteria.

5.1.1 Inclusion Criteria

1. Subject is male or non-pregnant female, 9 years of age or older. Females must be post-menopausal⁵, surgically sterile⁶, or using highly effective birth control methods.^{7,8} WOCBP must have a negative urine pregnancy test (UPT) at the Screening/Baseline Visit.
2. Subject has provided written informed consent/assent. A subject under 18 years of age must provide written informed assent and be accompanied by the parent or legal guardian at the time of assent/consent signing. The parent or legal guardian must provide informed consent for the subject. If a subject becomes 18 years of age during

⁵ Defined as amenorrhea greater than 12 consecutive months.

⁶ Hysterectomy, bilateral tubal ligation (at least six (6) months prior to study entry), or bilateral oophorectomy.

⁷ Highly effective contraception includes a) total abstinence, b) oral, injected, or implanted hormonal methods of contraception, c) intrauterine device (IUD), d) partner vasectomy (performed at least six (6) months prior to study entry), or e) double barrier methods of contraception [barrier methods include male or female condom, diaphragm with spermicidal foam/gel/film/vaginal suppository, cervical cap with spermicides, or contraceptive sponge].

⁸ Women of childbearing potential (WOCBP) include any female who has experienced menarche or is 10 years of age or older and who has not undergone successful surgical sterilization (hysterectomy, bilateral tubal ligation or bilateral oophorectomy) or is not postmenopausal [defined as amenorrhea >12 consecutive months]. WOCBP taking hormonal therapy for any reason exclusive of the treatment for acne (e.g., as contraception, etc.) must be on the same treatment for at least 12 weeks prior to study entry and must not change their dosing regimen during the study. Those who have used hormonal therapy prior to study entry must have discontinued use at least eight (8) weeks prior to the start of the study.

the study the subject must provide written informed consent at that time to continue study participation.

3. Subject has an Investigator's Global Assessment (IGA) score of 3 or 4 [0 (clear) to 4 (severe) scale].
4. Subject has facial acne vulgaris, (which can include the nose), with at least 30 to a maximum of 75 inflammatory lesions (papules, pustules, and nodules) and 30 to a maximum of 100 non-inflammatory lesions (open and closed comedones).
5. Subject and parent/guardian (if applicable) are willing to comply with study instructions and return to the clinic for required visits.
6. Subject has used the same type and brand of make-up, other facial products (exclusive of RX/OTC acne cleansers) and hair products (e.g., shampoo, gel, hair spray, mousse, etc.) for at least one (1) month prior to the Baseline Visit and agrees to continue his/her other general skin and hair care products and regimen for the entire study.

5.1.2 Exclusion Criteria

1. Subject is pregnant, lactating, or is planning to become pregnant during the study.
2. Subject has any skin pathology or condition that could interfere with the evaluation of the test products or requires the use of interfering topical or systemic therapy.
3. Subject has greater than two (2) facial nodules.
4. Subject has nodulocystic acne.
5. Subject has any condition which, in the investigator's opinion, would make it unsafe for the subject to participate in this research study.
6. Subject is currently enrolled in an investigational drug or device study.
7. Subject has received an investigational drug or has been treated with an investigational device within 30 days prior to the initiation of treatment (Baseline).
8. Subject has facial hair that could interfere with the study assessments in the opinion of the investigator.
9. Subject and parent/guardian (if applicable) are unable to communicate or cooperate with the investigator due to language problems, poor mental development, or impaired cerebral function.
10. Subject may be unreliable for the study including subjects who engage in excessive alcohol intake or drug abuse, or subjects who are unable to return for scheduled follow-up visits.
11. Subject has known hypersensitivity or previous allergic reaction to any of the active or inactive components of the test articles (see Section 6.1).
12. Subject has the need or plans to be exposed to artificial tanning devices or excessive sunlight during the trial.
13. Subject has used any of the following topical anti-acne preparations or procedures on the face:
 - Topical anti-acne treatments including, but not limited to, over-the-counter (OTC) acne cleansers or treatments, benzoyl peroxide, antibiotics, azelaic acid, sulfa

based products, corticosteroids and salicylic acid within two (2) weeks of the initiation of treatment.

- Retinoids, including tazarotene, adapalene, tretinoin, within four (4) weeks of the initiation of treatment.
- Light treatments, microdermabrasion, or chemical peels within eight (8) weeks of the initiation of treatment.

14. Subject has used the following systemic anti-acne medications:

- Corticosteroids (including intramuscular and intralesional injections) within four (4) weeks of the initiation of treatment. Inhaled, intranasal or ocular corticosteroids are allowed if use is stable (stable use is defined as dose and frequency unchanged for at least four (4) weeks prior to the initiation of treatment).
- Antibiotics within four (4) weeks of the initiation of treatment with the exception of five (5) days or less of antibiotic therapy during this period, BUT with no antibiotics use permitted within one (1) week prior to the initiation of treatment.
- Spironolactone within eight (8) weeks of the initiation of treatment with the exception of five (5) days or less of spironolactone therapy during this period, BUT with no spironolactone use permitted within one (1) week prior to the initiation of treatment.
- Retinoid therapy within six (6) months of the initiation of treatment.
- Other systemic therapy which may materially affect the subject's acne in the opinion of the investigator.

5.1.3 *Subject Withdrawal Criteria*

Procedures for handling subjects who are discontinued from the study are described in Section 13.2. Subjects who are discontinued will not be replaced.

6. TEST ARTICLES AND REGIMEN

6.1 Description

Test article name: CB-03-01 Cream, 1%
Active ingredient: Cortexolone 17 α -propionate (11-deoxy-hydrocortisone-17 α -propionate).
Other ingredients: Cetyl alcohol, glycerol monostearate, liquid paraffin, propylene glycol, tocopherol, sodium edetate, polysorbate 80, citric acid, purified water.

Placebo name: Vehicle Cream
Ingredients: Cetyl alcohol, glycerol monostearate, liquid paraffin, propylene glycol, tocopherol, sodium edetate, polysorbate 80, citric acid, purified water.

6.2 Instructions for Use and Application

At the first visit, the subjects will be instructed to wash their entire face (the area to be treated) with mild soap and water and then dry the area gently. The study staff will then instruct the subject and parent/guardian (if applicable) on how to dispense the cream, how much of the test article to use, and where to apply the assigned test article. The first application of cream should be applied in the office at Visit 1 under supervision of the study staff after subject has been deemed eligible. Typically, about 1 gram of the cream will be dispensed onto a fingertip and applied to the face by dabbing small amounts gently on multiple regions of the face (e.g., forehead, nose, cheeks, chin). Using a fingertip, the cream will be spread to provide a thin, uniform layer of the cream **over the entire face**.

Subjects and parents/guardians (if applicable) will be instructed to apply the cream to the whole face twice daily (morning and in the evening) for 12 weeks. The subject should ideally allow at least eight (8) hours between applications. All subjects should not wash the treated area for at least four (4) hours following test article application; and **MUST NOT APPLY THE TEST ARTICLE WITHIN FOUR (4) HOURS PRIOR TO ANY STUDY VISIT**.

Subjects will be provided with a Subject Diary to record the dates and time of application. Subjects will be instructed to only apply the study cream to the face as instructed by the investigator or designated study personnel. **Note: The dispensing, recording, and application of the test article by the subject may require adult supervision by the subject's parent/guardian.**

Subject and parent/guardian (if applicable) will also be provided with a Subject Instruction Sheet providing them with instructions on how to use and store the cream at home during the study period.

Subject and parent/guardian (if applicable) will be instructed to bring all the containers of cream (used and unused) and their completed diaries to each visit. The study staff will weigh all the returned containers and will record the weights on the appropriate study medication accountability logs and case report forms (CRFs).

Subjects who are not compliant with applying the creams as instructed (determined from subject diaries and/or the weight of test article used) may be discontinued from the study.

6.3 Warnings, Precautions and Contraindications

These test articles are for topical use only. Care should be taken to avoid contact with eyes and all mucous membranes. If contact with eyes occurs, rinse thoroughly with water.

Subjects with a known sensitivity to any of the ingredients in the test articles should not participate in this study.

Should skin irritation or rash develop, subjects should discontinue use and contact the study site.

In case of accidental ingestion, subjects should contact the investigator immediately.

The effects of the test article in nursing mothers, pregnant women and their unborn children are unknown. WOCBP must not be pregnant or planning a pregnancy during the study period.

7. RANDOMIZATION ASSIGNMENT

Subjects who are eligible for enrollment into the study will be randomized to receive CB-03-01 cream or vehicle cream in a 1:1 ratio. The randomization scheme will be blocked by investigational site. At each site, subject kits will be dispensed according to the kit number assigned by an IVRS/IWRS system as subjects are enrolled. At each site, the study staff will add the site number (provided to each site) and the subject number (starting with 001) to each kit label. The kit number dispensed to each subject will also be recorded on the source documents and CRFs. Treatment group designation will remain blinded until the final database is locked (unless unblinding is required as described in Section 15). Subjects who withdraw prematurely from the study will not be replaced.

8. PRIOR AND CONCOMITANT THERAPIES

Current medications and any medications taken in the 30 days prior to the start of the study (Screening, Visit 1) will be recorded on the appropriate CRFs with the corresponding indication. The medications to be recorded include RX and OTC medications (except vitamins and dietary supplements not used to treat a medical condition). All medications taken on a regular basis should be recorded on this page prior to commencing the use of the test article.

Therapies (medication and non-medication therapies) not restricted by the protocol may be used during the study for the treatment or prevention of disease or to maintain good health. Vitamins and mineral supplements are permitted at dosages considered by the investigator as reasonable for maintaining good health. Non-prohibited chronic therapies being used at Visit 1 may be continued. Any changes in concomitant therapies during the study must be recorded on the Concomitant Therapy Form. The reason for any change in concomitant therapies should be evaluated and, if appropriate, reported as, or in conjunction with, an adverse event.

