8.1 Prohibited Medications or Therapies

Medications or therapies that are prohibited during the duration of the study are as follows:

Prior to entry into the study, subjects must not use the medications and/or procedures on the face as specified in Section 5.1.2.

During the study, subjects must not use the following products and/or procedures on the face:

- Topical anti-acne treatments including, but not limited to, OTC acne cleansers or treatments, benzoyl peroxide, antibiotics, azelaic acid, sulfa based products, corticosteroids, and salicylic acid.
- Retinoids including tazarotene, adapalene, and tretinoin.
- Light treatments (including artificial tanning devices), microdermabrasion, or chemical peels.
- Any other investigational drug or use of any investigational device
- Systemic medications with potential anti-acne effects including:
 - Corticosteroids (including intramuscular and intralesional injections). Inhaled, intranasal, or ocular corticosteroids are allowed (see Section 8.2).
 - Antibiotics
 - Spironolactone
 - Retinoid therapy
 - The addition of hormonal contraception
 - Change to pre-existing hormonal contraception
 - Other systemic therapy, which may materially affect the subject's acne in the opinion of the investigator.

Other chronic medications being used at the time of Baseline Visit can be continued at the discretion of the investigator. The reason for any changes in such concomitant therapies should be reported as, or in conjunction with, an AE.

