### 6.2.1 Exclusion from the Per Protocol Set

Reasons for the exclusion from the Per Protocol Set include the following:

1. lack of compliance to the test article (subjects with an overall compliance not evaluable due to missing data or less than 80% as defined in paragraph 6.3);
2. exposure to an test article different from the one assigned to the subject;
3. lack of the primary variables assessments at Baseline or at Week 12;
4. failure to satisfy any inclusion/exclusion criteria (eligibility violations);
5. intake of prohibited medications.

The precise reasons for excluding subjects from the per protocol set will be fully defined and documented in the blind review meeting/conference report before breaking the blind.

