#### **6.6.14 Concurrent Therapies and Procedures**

Non medication concurrent therapies and procedures will be listed ([Listing 16.2.10.5](#)) by treatment group (CB-03-01 and Vehicle).

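### Comedone extraction is allowed by omission during the trial, although it directly removes lesions counted in P2 and may affect the IGA in P1

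*Protocol*

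**What the plan says.** Protocol Section 8 gives the default rule for concomitant treatment: "Therapies (medication and non-medication therapies) not restricted by the protocol may be used during the study for the treatment or prevention of disease". Whatever is not restricted is therefore available, non-drug therapies included.

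The restrictions are in two places. During the study, Section 8.1 bars these facial procedures: "Light treatments (including artificial tanning devices), microdermabrasion, or chemical peels". At entry, exclusion criterion 13 in Section 5.1.2 names the same three with a look-back: "Light treatments, microdermabrasion, or chemical peels within eight (8) weeks of the initiation of treatment".

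Section 8.1 also has two open-ended clauses. One covers topical care: "Topical anti-acne treatments including, but not limited to, OTC acne cleansers or treatments, benzoyl peroxide, antibiotics, azelaic acid", continuing with further products. The other leaves room for investigator judgement, but on systemic treatment only: "Other systemic therapy, which may materially affect the subject's acne in the opinion of the investigator". Intralesional steroid injection is barred under the systemic heading.

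SAP 6.2.1 gives five reasons for exclusion from the per-protocol set. Item 5 is "intake of prohibited medications". On procedures, SAP 6.6.14 says: "Non medication concurrent therapies and procedures will be listed", by treatment group. SAP 6.7.1 has no rule for Week 12 counts or IGA grades obtained after a procedure on the face.

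**The concern.** P2 is the change in open and closed comedones. Extraction, by hand or with an instrument, removes those lesions directly. A subject who has it shortly before Week 12 shows a lower count that owes nothing to the test article. The sponsor evidently regarded facial procedures as a threat to the assessments, since three are barred, yet one that acts directly on a counted lesion is not mentioned.

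The trial is blinded, so use should not follow knowledge of treatment. It may follow lack of response. If subjects with persistent comedones seek extraction more often, use would be higher on vehicle and the arms would be pulled together. At stake is the accuracy of the P2 estimate and, less directly, of P1, because the IGA grades are defined partly by non-inflammatory lesions.

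**Working it through.** **Does any clause reach extraction?**

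- Listed procedures (8.1 and exclusion 13): three are named and extraction is not among them.
- Topical clause (8.1): it is open-ended, but every example is a product.
- Investigator clause (8.1): it is limited to systemic therapy.
- Skin-care commitments (inclusion criterion 6 and Section 8.2): they concern products and regimen and do not name extraction.

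None clearly applies, so the Section 8 default governs.

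**Would the per-protocol set catch it?** The list in SAP 6.2.1 is not exhaustive, SAP 6.2 also removes major deviations, and Protocol 17.3 removes significant ones. A listed peel breaches 8.1 and can be excluded by that route. An extraction breaches nothing explicit, so its exclusion would depend on the blind review choosing to call a permitted act a deviation.

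**The plan's own P2 figure.** SAP 4.3.2 uses n = 2σ²(z_α/2 + z_β)² / Δ². With α = 0.05 two-sided and β = 0.033, the squared sum of quantiles is 14.428. With σ = 17 and Δ = 22 − 1 = 21:

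n = 2 × 289 × 14.428 / 441 = 18.9, so 19 per group, as stated.

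**Size of the shift.** The documents give neither a rate of use nor a number of lesions removed, so both are assumed. With 20 comedones removed per user and an additive effect, shift = (vehicle rate − active rate) × 20.

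| Use, vehicle vs active | Shift in P2 difference | Share of planned 21 |
|---|---|---|
| 5% vs 2% | 0.03 × 20 = 0.6 | 2.9% |
| 10% vs 4% | 0.06 × 20 = 1.2 | 5.7% |
| 15% vs 5% | 0.10 × 20 = 2.0 | 9.5% |

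The share is larger if the true difference is below 21. Equal use in both arms gives no shift, only added variance.

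**Effect on P2 power.** At 350 per group, SE = 17 × √(2/350) = 1.285. The largest shift in the table leaves 19 lesions, and 19 / 1.285 = 14.8 standard errors. Power stays above 99.9% even with a 20% excess on vehicle and 20 lesions removed, a shift of 4. With a shift of 2.0, power would drop below 90% only if the true difference were under about 3.24 × 1.285 + 2.0 = 6.2 lesions.

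**P3, under a different assumption.** Comedones are non-inflammatory, so extraction alone leaves P3 unchanged. If papules, pustules or nodules were also removed, P3 has less margin. Its planned difference is 5 (−15 vs −10 in the synopsis and SAP 4.3.3; Protocol 17.2 prints −14 and −11). The inputs with difference 5 reproduce the stated size: 2 × 289 × 14.428 / 25 = 333.6, so 334. A 10% excess on vehicle with 10 inflammatory lesions removed each cuts 5 to 4, and power at 350 per group falls from 97.3% to 87.6%. Nothing in the documents indicates such use.

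**The case against.** The best reply is that the silence is not complete and little depends on it. Inclusion criterion 6 commits subjects to their existing skin-care regimen, and Section 8.2 has that regimen approved before randomization, so starting facials mid-trial arguably departs from it. The Section 8 allowance is framed around disease and good health, so its application to a cosmetic facial can be disputed. Procedures are recorded and listed. All rates above are assumed, and the expected direction is against the product. The SAP also reports 732 subjects already enrolled, so a changed entry criterion could no longer affect entry.

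Most of this limits the size of the point. It does not supply a rule: a commitment on products and regimen does not tell a site whether extraction is allowed.

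Several stronger readings are tempting, and the documents do not support them:

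- *Prohibited procedures carry no per-protocol consequence because item 5 says medications.* The list is open, major deviations are also excluded, and reasons are settled at blind review before unblinding.
- *P2 could fail and block P3 and S1 to S4.* P2 power is essentially unaffected in every scenario tried.
- *P3 is affected by extraction.* Only if inflammatory lesions are removed as well.
- *Extraction before Baseline biases the comparison.* Treatment is randomized and the baseline count is a covariate, so no mechanism for a difference between arms is apparent.

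**Conclusion.** The gap is real and modest. Comedone extraction is permitted by omission, it acts directly on the P2 count, and neither the ITT analysis nor the per-protocol wording reliably deals with it. Under the assumed rates the P2 difference is understated by 0.6 to 2.0 lesions, or 3% to 10% of the planned 21, with no material loss of power. The expected direction is dilution, provided use is higher on vehicle. The documents give no evidence on that, nor on how often extraction occurs.

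P1 may move, but this cannot be sized. It is also limited, because IGA grade 1 restricts inflammatory lesions as well as comedones, so clearing comedones alone would not produce success.

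Separately, SAP 6.2.1 item 5 is narrower than Protocol 8.1, which restricts products and procedures too. The two should agree whatever is decided on extraction.

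**What to change.** 1. In the protocol, reconcile the Section 8 default with the lists in 8.1 and exclusion criterion 13, so that physical removal of counted facial lesions is handled with the other listed facial procedures. Any look-back is for the sponsor to set: the existing one is in exclusion 13 only, and 8.1 has none.
2. In SAP 6.2.1, change item 5 to *use of prohibited medications, products or procedures*, identified at blind review from the recorded concurrent procedures.

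The second change alone would make explicit that a listed peel counts, but it would not reach extraction unless the protocol lists are settled as well. It also affects only the per-protocol sensitivity set; the ITT analysis would still use the observed counts.

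The cost is a few words in two protocol lists and one SAP line, a slightly narrower allowance for subjects and a few more per-protocol exclusions. Concomitant procedures are already reviewed at each visit. A look-back on procedures might need an added baseline question, since Section 8 asks about the preceding 30 days for medications only.
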